6.1 Screening Phase

6.1.1 Screening Visit (Visit 0)

Subjects' eligibility will be confirmed during the screening phase. The below standard of care procedures will be conducted unless they occurred within four weeks prior to the screening visit as part of standard of care treatment.

- Standard Diagnostic Laboratory Tests (Appendix 15.4)
- Vital signs
- Radiological imaging (PET/CT or CT)
- Lipid panel

Review of concomitant medications

The below non-standard of care procedures will be conducted as part of the screening phase for all subjects:

- Informed consent: a signed and dated Institutional Review Board (IRB) approved informed consent form (ICF) that will be documented in the subject's source documents
- Pregnancy testing for females of childbearing potential
- Recording of demographic information (gender, date of birth, race, etc.) into electronic case report form (eCRF)
- Recording of medical history data and Laboratory Tests, as available, (Appendix 15.4) from medical records into eCRF

6.2 Intervention Phase

6.2.1 Baseline Visit (Visit 1)

The baseline visit should occur within 7 days of the screening visit, following confirmation of eligibility. The below standard of care procedures will be conducted unless they occurred within four weeks prior to Visit 0 as part of standard of care treatment.

- Physical exam including performance score
- Vital signs
- Lipid panel
- Review of concomitant medications

The below non-standard of care procedures will be conducted as part of Visit 1 for all subjects:

- Confirmation that subject meets inclusion criteria and does not violate any exclusion criteria, including confirmation by the Lead Principal Investigator
- GUID assigned
- Research blood draw
- Collection of fecal sample (optional)
- Recording of medical history data and Laboratory Tests, as available, (**Appendix 15.4**) from medical records into eCRF
- Dispensing of sirolimus loading dose (adults only)
- Dispensing of sirolimus daily dose

6.2.2 Visits 2 and 3

Subjects will visit the study center, or may visit their local medical provider or facility (e.g. Quest Diagnostics), 5 days \pm 2 days (Visit 2) and 2 weeks \pm 5 days (Visit 3) following administration of loading dose/first dose. The below non-standard of care procedures will be conducted as part of this study during Visits 2 and 3:

- Research blood draw
- Recording of medical history data and Laboratory Test, as available, (**Appendix 15.4**) from medical records into eCRF (at site)
- Phone assessment of AEs, study drug compliance, and review of medication changes
- Sirolimus Trough

Collection of fecal sample (optional – Visit 3 only)

6.2.3 Visit 4

Subjects will return to the study site 1 month \pm 1 week following administration of loading dose. At the physician's discretion, this visit may occur remotely and subject may visit their local medical provider or facility (e.g. Quest Diagnostics). The below procedures will be conducted as standard of care:

- Physical exam including performance score (if visit occurs on site)
- Vital signs (if visit occurs on site)
- Lipid panel
- Standard of Care Laboratory Tests (Appendix 15.4)
- Review of medication changes

The below non-standard of care procedures will be conducted as part of this study during Visit 4:

- Research blood draw
- Pregnancy testing for females of childbearing potential (may be self-administered by subjects if visit is conducted remotely)
- Sirolimus Trough
- Assess possible AEs
- Return of any non-consumed sirolimus (may be shipped if visit occurs remotely)
- Sirolimus pill count (if visit occurs on site)
- Dispensing of sirolimus daily dose (may be shipped if visit occurs remotely)
- Recording of medical history data, medication changes, AEs and Laboratory Test, as available, (Appendix 15.4) from medical records into eCRF

6.2.4 Visit 5

Subjects will visit the study center, or may visit their local medical provider or facility (e.g. Quest Diagnostics), 2 months \pm 2 weeks following administration of loading dose. The below non-standard of care procedures will be conducted as part of this study during Visit 5:

- Research blood draw
- Recording of medical history data, AEs, and Laboratory Test, as available, (Appendix 15.4) from medical records into eCRF (at site)
- Phone assessment of AEs, study drug compliance, and review of medication changes

6.2.5 Visit 6

Subjects will return to the study site 3 months \pm 2 weeks following administration of loading dose. It is highly encouraged that this visit occurs at the study site, but at the physician's discretion, this visit may occur remotely and subject may visit their local medical provider or facility (e.g. Quest Diagnostics). The below procedures will be conducted as standard of care:

- Physical exam including performance score (if visit occurs on site)
- Vital signs (if visit occurs on site)
- Radiological imaging (PET/CT or CT)
- Standard of Care Laboratory Tests (Appendix 15.4)
- Lipid panel

Review of medication changes

The below non-standard of care procedures will be conducted as part of this study during Visit 6:

- Research blood draw
- Pregnancy testing for females of childbearing potential (may be self-administered by subjects if visit is conducted remotely)
- Sirolimus Trough
- Assess possible AEs
- Return of any non-consumed sirolimus (may be shipped if visit occurs remotely)
- Sirolimus pill count (if visit occurs on site)
- Dispensing of sirolimus daily dose (may be shipped if visit occurs remotely)
- Intermediate assessment of primary objective
- Recording of medical history data, medication changes, AEs and Laboratory Test, as available, (Appendix 15.4) from medical records into eCRF

6.2.6 Visit 7 and 8

Subjects will visit the study center, or may visit their local medical provider or facility (e.g. Quest Diagnostics), 4 month \pm 2 week (Visit 7) and 5 month \pm 2 week (Visit 8) following administration of loading dose. The below non-standard of care procedures will be conducted as part of this study during Visit 7 and 8:

- Research blood draw
- Recording of medical history data, AEs and Laboratory Test, as available, (Appendix 15.4) from medical records into eCRF (at site)
- Phone assessment of AEs, study drug compliance, and review of medication changes

6.2.7 Visit 9

Subjects will return to the study site 6 month \pm 2 week following administration of loading dose. It is highly encouraged that this visit occurs at the study site, but at the physician's discretion, this visit may occur remotely and subject may visit their local medical provider or facility (e.g. Quest Diagnostics). The below procedures will be conducted as standard of care:

- Physical exam including performance score (if visit occurs on site)
- Vital signs (if visit occurs on site)
- Radiological imaging (PET/CT or CT)
- Standard of Care Laboratory Tests (Appendix 15.4)
- Lipid panel
- Review of medication changes

The below non-standard of care procedures will be conducted as part of this study during Visit 9:

- Research blood draw
- Collection of fecal sample (optional)
- Pregnancy testing for females of childbearing potential (may be self-administered by subjects if visit is conducted remotely)
- Sirolimus Trough
- Assess possible AEs

- Return of any non-consumed sirolimus (may be shipped if visit occurs remotely)
- Sirolimus pill count (if visit occurs on site)
- Dispensing of sirolimus daily dose (may be shipped if visit occurs remotely)
- Intermediate assessment of primary objective
- Recording of medical history data, medication changes, AEs and Laboratory Test, as available, (**Appendix 15.4**) from medical records into eCRF

6.2.8 Visit 10 and 11

Subjects will visit the study center, or may visit their local medical provider or facility (e.g. Quest Diagnostics), 7 month \pm 2 week (Visit 10) and 8 month \pm 2 week (Visit 11) following administration of loading dose. The below non-standard of care procedures will be conducted as part of this study during Visits 10 and 11:

- Research blood draw
- Recording of medical history data, AEs and Laboratory Test, as available, (Appendix 15.4) from medical records into eCRF (at site)
- Phone Assessment of AEs, study drug compliance, and review of medication changes

6.2.9 Visit 12

Subjects will return to the study site 9 month \pm 2 week following administration of loading dose. It is highly encouraged that this visit occurs at the study site, but at the physician's discretion, this visit may occur remotely and subject may visit their local medical provider or facility (e.g. Quest Diagnostics). The below procedures will be conducted as standard of care:

- Physical exam including performance score (if visit occurs on site)
- Vital signs (if visit occurs on site)
- Radiological imaging (PET/CT or CT)
- Standard of Care Laboratory Tests (Appendix 15.4)
- Lipid panel
- Review of medication changes and updates

The below non-standard of care procedures will be conducted as part of this study during Visit 12:

- Research blood draw
- Pregnancy testing for females of childbearing potential (may be self-administered by subjects if visit is conducted remotely)
- Sirolimus Trough
- Assess possible AEs
- Return of any non-consumed sirolimus
- Sirolimus pill count (if visit occurs on site)
- Dispensing of sirolimus daily dose
- Intermediate assessment of primary objective
- Recording of medical history data, medication changes, AEs, and Laboratory Test, as available, (Appendix 15.4) from medical records into eCRF

6.2.10 Visits 13 and 14

Subjects will visit the study center, or may visit their local medical provider or facility (e.g. Quest Diagnostics), 10 month \pm 2 week (Visit 13) and 11 month \pm 2 week (Visit 14) following administration of loading dose. The below non-standard of care procedures will be conducted as part of this study during Visits 13 and 14:

- Research blood draw
- Recording of medical history data, AEs and Laboratory Test, as available, (Appendix 15.4) from medical records into eCRF (at site)
- Phone assessment of AEs, study drug compliance, and review of medication changes

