3.1 General Design

This study is a Phase II open label study of daily administration of sirolimus in up to 24 evaluable male or female adults. Up to 40 subjects may be enrolled, defined as providing informed consent for the trial, to obtain this target of evaluable subjects. An interim analysis will be conducted after 14 subjects have completed the Visit 9 intermediate assessment. The mechanism of action of sirolimus in clinically active iMCD will also be examined.

Adult subjects will receive a sirolimus loading dose of 5 mg/m², rounded to the nearest mg, on day 1. Loading dose may be lower at the discretion of the prescribing physician. Starting on day 2, adult subjects will take sirolimus daily at 2.5 mg/m²/day (rounded to the nearest mg), adjusted to a target trough level of 10-15 ng/mL. Pediatric subjects will not receive a loading dose, and daily dosing will be at 2 mg/m²/day (rounded to the nearest mg), adjusted to achieve a target trough level of 5-15 ng/mL. (see **Section 5.2, Intervention Regimen**). Given that sirolimus is extensively metabolized by CYP3A4, sirolimus dosing for subjects receiving strong CYP3A4 inhibitors or inducer therapy (https://drug-interactions.medicine.iu.edu/main-table.aspx) should be monitored carefully and adjusted accordingly. Additionally, sirolimus trough levels should be monitored if patients are started on or if their CYP3A4 therapy is altered, and sirolimus dosing adjusted to maintain trough levels of 10-15 ng/mL (5-15 ng/mL in children). The dosing of adult patients who weigh less than 40 kg should be adjusted, based on body surface area, to 3

mg/m² for the loading dose and 1 mg/m²/day daily. It is recommended that the licensed site investigator reduce maintenance dose in patients with hepatic impairment.

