Subjects who meet all inclusion criteria and do not violate any exclusion criteria will be determined eligible for enrollment into the study by the licensed site investigator. The Lead Principal Investigator will confirm the subject's eligibility. During the Intervention Phase (12 ± 1 month), subjects will visit their study site at regular intervals to assess any changes in health status, medication, study drug compliance, and treatment response. They will also be monitored remotely by their licensed site investigator through lab testing performed as per standard of care at local healthcare facilities. During the Follow Up Phase, 12 ± 2 weeks following the End of Treatment Visit, site study staff will contact subjects by phone. Peripheral blood will be collected at baseline and at regular intervals during the Intervention Phase for research purposes. Subjects will be asked to provide their consent to allow any biological samples collected as part of this study or collected during their enrollment period in this study, but for purposes outside of the study, to be used for laboratory research purposes, including genetic sequencing studies. Subjects will also be asked to provide their consent to allow any biological samples from their past medical procedures to be used for laboratory research purposes, including genetic sequencing studies.

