6.5 Unscheduled Visits

An unscheduled visit may be required to repeat a laboratory assay or to conduct further safety evaluation. Enrollment into this study places no restrictions upon subjects' ability to visit their physician outside of the study's scheduled visits. Health data generated from such visits will be incorporated into the eCRF at the time of the subject's next scheduled visit.

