7.4 Laboratory Evaluations

Blood sampling will be performed for this study for the following laboratory evaluations. Other laboratory tests will be collected as part of standard of care treatment and recorded in the eCRF from medical record review.

- Sirolimus trough levels
- Pregnancy testing (if applicable)
- Lipid panel (if not collected as standard of care)

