12.1 Risks

The risk to patients of exposure to the treatment intervention, sirolimus, as related to AEs is relatively low. Sirolimus is an FDA-approved therapy with an established safety profile. Although uncommon, AEs are possible and will be monitored by study staff and licensed site investigators. The most common (≥20%) adverse reactions reported for sirolimus 2 mg/day at a higher incidence than reported for placebo include:

- peripheral edema
- hyperlipidemia, hypercholesterolemia, hypertriglyceridemia
- increased creatinine
- constipation
- hypertension
- abdominal pain / diarrhea
- headache
- arthralgia

Other less common serious complications include:

- angioedema
- leucopenia
- thrombocytosis / thrombocytopenia
- fluid accumulation

- impaired wound healing
- proteinuria
- interstitial lung disease/non-infectious pneumonitis
- calcineurin inhibitor-induced hemolytic uremic syndrome/thrombotic thrombocytopenic purpura/thrombotic microangiopathy

The below table summarizes the known adverse events (AEs) categorized based on timing and frequency:

Known Adverse Events (AEs)									
	Common	Occasional	Rare						
	21-100 out of every 100	5-20 out of every 100	<5 out of every 100						
Immediate: 1-2 days of receiving drug	Nausea, vomiting, oral ulcers	Rash	Allergic reaction (may be life threatening)						
Prompt: 2-3 weeks on drug	Increased cholesterol, increased blood pressure, decreased kidney function, diarrhea	Infections, swelling, weight gain, muscle/joint pain, tremor, acne, rash, abdominal pain, mucositis, headache	Decreased red and white blood cells generated in bone marrow, decreased liver function						
Delayed: Any time later during therapy, excluding the above conditions	Acne		Malignancy resulting from this treatment, destruction of red blood cells and decreased kidney function, interstitial lung disease, hemolytic uremic syndrome/thrombotic thrombocytopenic purpura*						
Late: Any time after completion of treatment			Interstitial lung disease						
Sirolimus was embryo/feto toxic in rats at dosages of 0.1 mg/kg and above (approximately 0.2 to 0.5 is the clinical doses adjusted for body surface area). Embryo/feto toxicity was manifested as mortality and reduced fetal weights (with associated delays in skeletal ossification). Sirolimus is excreted in trace amounts in milk of lactating rats. It is not known whether sirolimus is excreted in human milk.									

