tacrolimus. Incre		other medications, including hibitor-induced hemolytic ure ombotic microangiopathy							

To monitor for these risks, blood pressure will be monitored from standard of care physical exams. Additionally, fasting serum lipids will be monitored from standard of care lipid panels. Treating physicians may consider use of a cholesterol-lowering agent, such as an HMG-CoA reductase inhibitor, in patients with elevated cholesterol, especially those who have responded to therapy and may be on the drug for 6 months or longer. HMG-CoA reductase inhibitors that are also

CYP3A4 inhibitors (https://drug-interactions.medicine.iu.edu/main-table.aspx) should be avoided. Sirolimus can sometimes impair kidney, liver and bone marrow function. Kidney, liver and bone marrow function will be monitored from standard of care metabolic, liver function and complete blood counts panels.

In general, immunosuppressive therapy may result in an increased risk of development of lymphoma and other malignancies. Such risks will be monitored for by review of subjects' complete blood counts (CBC) and imaging for evidence of malignancy. Additionally, patients receiving immunosuppressants, including sirolimus, are at increased risk for opportunistic infections, including polyoma virus infections. Polyoma virus infections in immunosuppressed patients may have serious, and sometimes fatal, outcomes. These include polyoma virus-associated nephropathy (PVAN), mostly due to BK virus infection, and JC virus-associated progressive multifocal leukoencephalopathy (PML) which have been observed in patients receiving sirolimus.

There is a risk of breach of confidentiality in that someone could trace the information in the research database back to an individual. The risk that someone will identify an individual is very small as data will be stored on a secure database on password protected computers and no personal health information will be entered into the database; subjects will be tracked using a GUID assigned at enrollment. Only designated study staff at the subject's site of enrollment will have access to the master electronic list linking personal identifiers to the subject's GUID.

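### Section 12.1 lists kidney, marrow and liver effects at 2-3 weeks on drug, but the first panel the protocol requires after dosing is at Visit 4 (about days 23-37); a panel at Visit 3 would be a cheap improvement

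*Combined protocol and SAP*

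**What the plan says.** The adverse event table in section 12.1 has a row labelled "Prompt: 2-3 weeks on drug". It places decreased kidney function in the common column (21-100 of every 100) and decreased marrow production and decreased liver function in the rare column (fewer than 5 of every 100). The text after the table states the monitoring plan: "Kidney, liver and bone marrow function will be monitored from standard of care metabolic, liver function and complete blood counts panels". It gives no dates.

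Section 6.2.2 sets Visit 2 at 5 ± 2 days and Visit 3 at 2 weeks ± 5 days. Its list opens with "The below non-standard of care procedures will be conducted as part of this study during Visits 2 and 3" and contains a research draw, a sirolimus trough, a phone assessment of adverse events, compliance and medication changes, and the recording of whatever Appendix 15.4 results are available. Section 6.2.3 then names Standard of Care Laboratory Tests at Visit 4, 1 month ± 1 week. Appendix 15.4 defines these as items 1-11, which include the blood count with differential (item 1), the basic metabolic panel with creatinine/eGFR (item 4) and liver function tests (item 9).

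Three other places bear on early laboratory data:

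- Section 3.1: subjects are also followed remotely "through lab testing performed as per standard of care at local healthcare facilities".
- Section 7.4 lists troughs, pregnancy tests and, if needed, lipids as study-drawn tests, and adds: "Other laboratory tests will be collected as part of standard of care treatment and recorded in the eCRF from medical record review".
- Section 6.5: "An unscheduled visit may be required to repeat a laboratory assay or to conduct further safety evaluation".

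**The concern.** The plan names a period in which it expects kidney, marrow and liver effects, and the first panel it requires falls after that period. Early changes in creatinine, transaminases or counts are often silent, so a phone check would not be expected to reveal them.

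The troughs on about days 5 and 14 can also lead to dose changes before any on-drug panel is required. Section 5.2 asks the investigator to weigh clinical toxicity when adjusting the dose, and section 3.1 says: "It is recommended that the licensed site investigator reduce maintenance dose in patients with hepatic impairment". A current panel alongside the day-14 trough would inform both. What is at stake is the timeliness of safety information for individual subjects, not the efficacy estimate.

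**Working it through.** The plan has no figure of its own to reproduce here; the check is day arithmetic on the visit windows. Visit contents come from sections 6.2.2 and 6.2.3 rather than from column positions in the 15.3 calendar.

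**Inputs.** Onset band: 2-3 weeks, read as days 14-21 (12.1). Visit 2: 5 ± 2 days. Visit 3: 14 ± 5 days. Visit 4: 1 month ± 7 days. The length of a month is not defined, so 28, 30 and 31 days are shown.

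**Windows.**
- Visit 2: 5 − 2 = 3 to 5 + 2 = 7.
- Visit 3: 14 − 5 = 9 to 14 + 5 = 19.
- Visit 4, 30-day month: 30 − 7 = 23 to 30 + 7 = 37.
- Visit 4, 28-day month: 21 to 35. Visit 4, 31-day month: 24 to 38.

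**First required panel against the end of the band (day 21).**
- 30-day month: 23 − 21 = 2 to 37 − 21 = 16 days after it closes.
- 28-day month: 0 to 14 days. 31-day month: 3 to 17 days.

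Only a 28-day month with the earliest permitted visit touches the band.

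**Distance from a Visit 3 panel to the Visit 4 panel.**
- Nominal: 30 − 14 = 16 days (14 with a 28-day month, 17 with a 31-day month).
- Range over both windows, 30-day month: 23 − 19 = 4 to 37 − 9 = 28 days. Across 28- to 31-day months: 21 − 19 = 2 to 38 − 9 = 29 days.

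**How often a Visit 3 draw would follow onset.** These are distances between visits, not gains in detection. As an illustration, assume that onset is equally likely on each of the 8 days 14-21, that the draw is equally likely on each of the 11 days 9-19, and that a draw on the day of onset counts. For onset on days 14 to 19 there are 6, 5, 4, 3, 2 and 1 draw days on or after onset; for days 20 and 21 there are none. The sum is 21, so the proportion is 21 / (8 × 11) = 21/88 = 24%. If the draw is kept to days 14-19 (6 days), the same count gives 21 / (8 × 6) = 21/48 = 44%. This is why a draw on day 14 or later is preferable. In the remaining cases the effect would still first show at Visit 4.

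**The case against.** The strongest reply is that this is a deliberate design. The list at Visits 2 and 3 covers only procedures outside standard of care, while 12.1 assigns organ monitoring to standard of care, which 3.1 says is done locally and reviewed by the site investigator. Results are recorded where available, there is phone contact and a trough at both visits, and unscheduled safety visits are allowed. Subjects who stop before Visit 4 have the panel at the Early Termination Visit. The documents do not say how often local panels are drawn in the first month, so the practical gap may be small. All of this stands, and it limits the point to a low-cost improvement. It does not close the gap, because none of these routes is dated or requires a panel.

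The background also tempers the risk. Section 1.2.2 speaks of little nephrotoxicity and mild myelosuppression, and 1.2.2.2 reports renal function not worse in the transplant trials, although it names thrombocytopenia among the major side effects. Organ function is also checked at screening, with exclusion limits in 4.2. That gives a value before dosing but not one on drug.

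Three stronger readings are tempting, and the documents do not support them.

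- **A Visit 3 panel means detection 16 days earlier.** It does not. Five of the 11 permitted days (9-13) precede the listed band, and effects that start after the draw are not caught by it.
- **The dosing rule takes renal function as an input.** Section 5.2 mentions a change in renal function as something that can alter the sirolimus level and so prompt re-measurement, not as a term in the dose.
- **Blood pressure has the same gap.** Section 12.1 says "blood pressure will be monitored from standard of care physical exams", and 6.2.2 lists no vital signs at Visits 2 and 3. But 7.3, taken literally, has vital signs assessed at every visit, so it cannot be said that no early reading is planned.

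**Conclusion.** The point holds as a cheap safety improvement. Under the section text, the first blood count, metabolic and liver panel required after dosing is at Visit 4, 2-16 days after the listed 2-3 week band closes (30-day month). A Visit 3 panel would supply a required on-drug value nominally 16 days sooner, available when the day-14 trough is read. The gain is nil for a subject whose local labs are already drawn by then, and the documents do not allow that share to be estimated.

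This rests on two assumptions: a month of about 30 days, and the row label meaning onset during days 14-21. If the label means at any time within the first 2-3 weeks, effects could already be present at Visit 3 more often than the 24% or 44% illustrations suggest. Of the three organ effects, only the kidney effect is listed as common. A reader might infer that the plan breaks its own monitoring commitment or leaves subjects unmonitored. It does neither: 12.1 promises standard of care panels without dates, and the schedule is consistent with that.

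**What to change.** Add Appendix 15.4 items 1, 4 and 9 to Visit 3, drawn with the clinical trough sample already taken there:

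- **6.2.2:** one line listing the panel at Visit 3, preferably drawn on day 14 or later within the existing day 9-19 window, with a local panel drawn within that window accepted in its place.
- **15.3:** the matching mark at Visit 3.
- **7.4:** one line adding the panel to the tests drawn for the study where it is not available from standard of care.

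Visit 2 can stay as it is, since days 3-7 precede the listed band. Describe the benefit as a required on-drug safety value at about week 2, not as earlier detection by a fixed number of days.

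The cost is a short amendment and one routine panel per subject: 24 for the evaluable target and at most 40 if enrollment reaches its ceiling. No new visit or needle stick is needed, and the 55 mL limit in section 6 applies to research blood, so a clinical panel does not count against it.
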